4.3.3 R00 Phase Pilot RCT Procedures

The R00 phase study is a pilot randomized controlled trial (RCT) of 6 months duration. Participants will be randomized to one of 2 arms (n=30 each): 1) wait-list control; or 2) SMS intervention. The study will include 3 measurement visits, baseline, 3, and 6 months. Patients will be paid \$30 for each measurement visit.

Upon receiving the referral list (interested patient's name and phone number) from the providers, the bilingual study staff will call the patient and provide more details about the study. If patients expressed interest in participation, the study staff will administer several screening questions over the phone. After eligibility is determined and verbal consent is obtained, we will collect baseline surveys over the phone and randomize them via a computer-generated randomization scheme with equal allocation to one of the 2 groups: 1) wait-list control; or 2) SMS.

Independent variable: randomization arm

Wait-list control group: All participants will continue to receive the standard of usual care for their T2D at their providers' office during the course of our study. At the end of the study, the wait-list control group will be provided the opportunity to receive the counseling videos delivered to them via SMS links.

SMS intervention: Participants in the intervention group will receive SMS-based video counseling, which include both educational and SCT-based behavioral content (see Table 1 below for a tentative outline of the intervention content). Given the system and personal barriers, we believe this SMS-based approach will improve access to culturally and linguistically tailored diabetes counseling. Additionally, this approach will allow participants to review the videos later on or share with their loved ones who often want to be supportive but do not know how. We will send 2 videos each week for a total of 12 weeks with each video about 5-10 minutes in duration. The videos will be sent via WeChat or regular text messages (SMS). We will contact participants mainly through phone calls from an NYU Langone Study Phone. WeChat will be only used to send the health education videos. No other communication will occur via WeChat. Our study team will remind participants at the beginning of the study and

during the bi-weekly phone calls about not sending any Protected Health Information via WeChat. In addition, our education videos do not contain any Protected Health Information and it will teach participants about diet, exercise, and stress management in general. We will ask participants' permission to use WeChat platform and advise that sending messages over an unsecured application like WeChat is an unsecure and unencrypted form of communication and there is a potential risk of disclosing information to an individual who is not authorized to receive it (unauthorized disclosure).

We will also let participants know that they can still participate in the study if they decline to receive the health education videos on WeChat. As an alternative, we will send the education videos as regular text messages to their phones. They can decline at any time during the study to receive the videos on WeChat and then we will switch to regular text messages.

We will also help participants to set goals for their diabetes management and then have biweekly phone call follow-ups to check in their progress toward the goal and problem solve any raised questions/concerns.

Table 1: Tentative Outline of the Intervention Content

| Sess. # | Education Materials | Social Cognitive Theory-Based Behavioral Materials |
|---------|--|--|
| 1 | Overview of diabetes, self-management | Setting goals; Establishing the relevance of behavior change. |
| 2 | T2D diet, healthy eating, portion control | Self-Reward. Turning goals into habits. |
| 3 | Glucose self-monitoring | Social support. Developing and working your social support network |
| 4 | Medication management | Problem solving: Barriers and setbacks. Problem solving model. |
| 5 | Exercise and diabetes; home exercise demo | Problem solving: Behavioral triggers and stimulus-control |
| 6 | Attending doctor appointments | Problem solving: Lapse and Relapse |
| 7 | Chinese holidays and eating at restaurants | Problem solving: Coping with lapses and setting new goals |
| 8 | Stress and T2D | Problem solving: Stress management. |
| 9 | Grocery shopping demo at Chinese grocery store | Problem solving: Cutting carbohydrates and finding replacements |
| 10 | Healthy cooking demo for a Chinese diet | Problem solving: Eliminating negative self-talk |
| 11 | Navigating the US healthcare system | Problem solving: Cravings for white rice, noodle, bun, dumplings etc |
| 12 | Review of lifestyle recommendations | Problem solving: Anticipating high-risk situations |

Procedures: The study will include 3 measurement phone calls, baseline, 3, and 6 months. Patients will be paid \$30 for each measurement call. Due to COVID-19, all data will be collected over the telephone. Each survey calls will include audio/Video recordings if verbal consent from the study participants was obtained. For participants randomized to the SMS intervention group, we will reimburse \$5 each week to each participant for cell phone data usage if they finish viewing both of the sent videos for that week. Given that we will send videos over a total of 12 weeks, participants may expect to receive a range of \$0-\$60 ($=\$5*12$) depending on the number of weeks they have completed the videos. We will also provide \$60 to control participants if they finish all study related procedures at 3 months assessment.

Study Variables

covariates

[figure not shown]

Figure 1. Conceptual Model

Primary & Exploratory Outcomes

Primary outcome: HbA1c: As part of the usual care, patients with T2D receive a HbA1c blood test at their doctors' office every 3-6 months. To minimize participants' burden, we will not conduct additional blood tests for this study. Instead, we will abstract the HbA1c testing results from the medical record at the participant's health care facility. Once we obtain the consent from participants, we will contact their doctors' offices for HbA1c results.

Secondary outcomes: Consistent with our conceptual model (Fig. 1), we will also measure self-efficacy, diabetes self-management behaviors, dietary intake, and physical activities at each time points (baseline, 3-, and 6-months). All of these scales have been used and validated in the Chinese population.

1. **Self-efficacy:** We will use the well-validated Stanford Diabetes Self-Efficacy Scale⁴² to measure participants' confidence to manage T2D. This instrument contains 8 items and asks participants to rate their confidence level in performing specific self-management behaviors, using 10-point Likert scale ranging from 1 (not at all confident) to 10 (totally confident).
2. **Diabetes Self-Management Behaviors:** We will administer the adapted Summary of Diabetes Self-Care Activities (SDSCA) measure⁴³ to assess participants' adherence to diabetes self-management behaviors. This scale consists of 13 items and asks participants to describe their diabetes self-care activities over the past 7 days.
3. **Dietary Intake:** Informed by a previous study in Chinese Americans,⁴⁴ we will use the adapted Mediterranean Dietary Screener⁴⁵ to estimate dietary intake behaviors in our participants at baseline, 3- and 6-months.
4. **Physical Activity:** We will use the International Physical Activity Questionnaire (IPAQ)^{46,47} short version to assess the frequency and duration of various physical activities undertaken by adults over the past 7 days. This scale will provide an estimate of the number of minutes per week participants engage in each category of physical activity (e.g., vigorous, moderate, and mild intensity). We will also use the ActiGraph to objectively measure physical activity and sleep. Our study staff will distribute and collect the device to participants once they are eligible for the study. Once we receive the device, we will download the data.

Covariates: Sociodemographic, health characteristics, and acculturation. We will use a sociodemographic questionnaire to collect basic information about the participant such as age, gender, education, income, duration of residence in the US, health insurance, the diabetes medication regimen, duration of T2D, and medical history. Informed by prior literature, we will also include surveys to measure Health Beliefs, Diabetes Knowledge, Diabetes Distress, Social Support, Mental Health, the Impact of COVID-19, and memory test, which also play essential roles in diabetes management.

Rutgers Pilot Mental Health and Psychosocial Related Surveys: Accumulating evidence shows that patients with T2D are more likely to have mental health issues, including depression, anxiety, diabetes distress, and other mental health issues than those without the disease. We will add several mental health and psychosocial related surveys and administer this survey to the study participants via telephone at one survey only.. This survey phone call will not be audio or video recorded but the consent process will be audio recorded. We are going to use validated measures to assess general stress,^{48,49} acculturation,⁵⁰ minority stress (discrimination),⁵¹ symptoms of depression,^{52,53} anxiety,⁵⁴ loneliness,⁵⁵ social support,^{56,57} stigma towards mental health⁵⁸, mindfulness^{59, 60}, and mental health seeking behaviors. See Table 2 below. We will provide a \$20 clincard incentive to participants who complete this survey with us.

Rutgers Pilot Focus Groups (N=10-16): We will select 10-15 participants based on their mental health survey responses to join the focus groups (2 focus groups; 5-8 participants per group) to gain a deeper understanding of barriers to utilizing mental health services. Participants who reported elevated stress, anxiety or depressive symptoms will be invited for this focus group discussion. We will collect their AV consent to record the focus group discussion. We will also ask participants' preferences for mental health support (e.g., individual vs. group-based, in-person vs. phone vs. video-based). Participants will receive additional \$20 clincard incentive for their time. We will submit the interview guide as a modification later.

Table 2. Mental health and psychosocial related surveys

| Variables | Surveys/Scales | Any Adaptations? |
|--|--|---|
| General stress | Perceived Stress Scale | Validated scale |
| Acculturation | Short Acculturation Scale for Hispanics | Adapted from the Hispanics version. In the response options, we changed "Spanish" to "Chinese". |
| Minority stress | Everyday Discrimination Scale | Validated scale |
| Depressive symptoms | PHQ-9 | Validated scale |
| Anxiety | Hospital Anxiety and Depression Scale (HADS) | Validated scale |
| Loneliness | Revised UCLA Loneliness Scale | Validated scale |
| Social support | Social support Availability Online social support | Validated scales |
| Stigma towards Mental Health | Perceived Devaluation and Discrimination Scale | Validated scales |
| Current and Past Mental Health Seeking Behaviors | Self-developed | Investigator developed |
| Mindfulness | FFMQ-15 | Validated scales |

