2.2 Aims

K99 phase

Primary Aim 1a: Characterize barriers and facilitators of glycemic control in Chinese Americans with T2D

Primary Aim 1b: Develop culturally and linguistically tailored SMS intervention content

Primary Aim 1c: Assess the feasibility and acceptability of the SMS intervention

R00 phase

Primary Aim 2a: Establish the proof-of-concept regarding the efficacy of the SMS intervention for glycemic control in Chinese Americans with T2D

Exploratory Aim 2b: Explore the potential effects of the SMS intervention on psychosocial and behavioral factors in glycemic control.

Rutgers Mental Health Pilot

Exploratory Aim 2c: Examine current mental health burden and psychosocial support and how they are related to diabetes self-care behaviors and glycemic control in Chinese Americans with T2D (via validated surveys)

Exploratory Aim 2d: Characterize barriers to accessing mental health services and understand needs and preferences in Chinese Americans with T2D (via focus groups)

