Phase 2 R00 Phase pilot RCT Exclusion criteria: Individuals will be excluded from participation if they meet any of the following: (1) unable or unwilling to provide verbal consent; (2) unable to participate meaningfully in the intervention (e.g., uncorrected sight and hearing impairment); (3) unwilling to accept randomization assignment; (4) pregnant, plans to becomes pregnant in the next 6 months, or who become pregnant during the study, or (5) breastfeeding or (6) live in a facility or other health care setting where they have no control over diabetes self-management.

Rutgers Mental Health Pilot: For the quantitative survey, because we will call K99, R00 phase (s18-00609), and FAMILY study (s19-01275) participants, the inclusion and exclusion criteria will be the same as each parent study. In addition, participants are eligible to participate in this pilot if they are willing to answer additional mental health related questions. For the focus group participants, we will review the mental health survey responses from participants and invite those who reported elevated stress, anxiety or depressive symptoms to join the focus group discussion.

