6. CONFIDENTIALITY AND DATA STORAGE

We will use the IRB recommended RedCap for data storage (openREDCap.nyumc.org). We will also work with MCIT to set up a NYU shared network drive which is HIPAA compliant (for offsite backup storage) specifically for our study. All study personnel have already taken the mandatory HIPAA and Patient Privacy/Confidentiality training modules required by our institutional IRBs, to ensure that they are aware of the importance of patient confidentiality and all appropriate laws regarding protection against privacy breaches. Procedures will be in place to ensure that all files containing subject information will be kept in locked filing cabinets or password-protected electronic databases on a secure server. The majority of study data and all interview transcripts will be maintained in electronic files with no patient identifiers other than a study ID number; there will be one file maintained separately with its own password protection that links study ID numbers to patient identifying information.

No identifiable information about study participants will be disclosed to individuals outside those approved by the IRB to be on the study protocol. No publications that result from the study will identify individual participants.

Transcript files will also be password-protected and user-restricted. We will delete potential identifiable information from transcripts and audio recordings one year after the study ends. We will also encourage participants to use pseudonyms during focus groups and/or interviews. During each focus group or interview session, the study PI will emphasize the importance of privacy and confidentiality of the discussion within the group. The text-message-based video counseling will be protected via password-enabled access. Only study participants will have access codes to open these videos. Others in the same household would not be able to open the video, unless participants choose to share the access code.

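### Preference for individual or group mental health support is asked only of people who agree to join a group; ask it of every survey respondent instead

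*Combined protocol and SAP*

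**What the plan says.** Section 2.2 sets Exploratory Aim 2d of the Rutgers Mental Health Pilot: "Characterize barriers to accessing mental health services and understand needs and preferences in Chinese Americans with T2D (via focus groups". Focus groups are the only data source named for it, and Section 7.1 analyzes it by thematic analysis of those groups alone.

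Section 4.3.3 lists what the groups will be asked, including "preferences for mental health support (e.g., individual vs. group-based, in-person vs. phone vs. video-based". Section 3.1 says the same. The entry rule in Section 4.3.3 is "Participants who reported elevated stress, anxiety or depressive symptoms will be invited for this focus group discussion", and Section 3.3 repeats it. The format is "2 focus groups; 5-8 participants per group", with consent sought for audio and video recording.

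The survey that precedes the groups is a single one-to-one telephone call, unrecorded apart from consent, with a target of 133 respondents. Section 3.1 starts it once the pilot modification is approved. Section 4.3.3 leaves the focus-group interview guide to a later modification.

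**The concern.** One of the things to be learned is whether people want support alone or in a group. To give a view, a person must first agree to discuss mental health in a recorded group. Willingness to enter is plausibly related to the answer, which is a different problem from the ordinary limits of a small qualitative sample. People who would rather be seen individually, or who are wary of stigma, are plausible decliners, and the plan describes no way of hearing them.

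The aim is also worded for Chinese Americans with type 2 diabetes in general, whereas those heard are respondents with raised scores who accepted a group. What is at stake is how far the preference findings transfer to people outside the room.

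**Working it through.** **Is there another route to the preference answer?**

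- Survey instruments (Section 4.3.3, Table 2): stress, acculturation, discrimination, depression, anxiety, loneliness, social support, stigma, mindfulness, and a self-developed module on current and past help-seeking. None is listed as a preference item. The items of the self-developed module are not shown, so it could contain one, but the plan does not say so.
- Individual interviews for this pilot: none described.
- Log of refusals, or comparison of attenders with decliners: none described in Section 7.1.
- By contrast, the K99 phase allowed focus groups or interviews (Sections 3.1 and 4.3.1) and planned a separate group for poorly engaged participants (Section 4.3.2). The team has sought out less engaged voices before.

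**Reproducing the plan's numbers**

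- Focus groups: 2 × 5 = 10 and 2 × 8 = 16, which matches the stated N of 10-16. The adjoining sentence, "We will select 10-15 participants based on their mental health survey responses", gives 15 as the upper limit. This small mismatch should be tidied but does not affect the point.
- Survey: 20 + 30 + 60 + 23 = 133, as stated.
- Share of the survey target asked about preference: 10/133 = 7.5% to 16/133 = 12.0%.

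**How large could a tilt be?** Let p be the true share of invitees preferring group support. Let r be the acceptance rate among those who prefer groups divided by the rate among those who prefer individual support. The share among attenders is

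p × r / (p × r + 1 − p).

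The documents give neither p nor r, so every value below is an assumption.

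| True group preference | r = 1 | r = 1.5 | r = 2 | r = 3 | r = 4 |
|---|---|---|---|---|---|
| 20% | 20% | 27% | 33% | 43% | 50% |
| 30% | 30% | 39% | 46% | 56% | 63% |
| 50% | 50% | 60% | 67% | 75% | 80% |

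For example, with p = 0.3 and r = 2: 0.6 / (0.6 + 0.7) = 0.46. At r = 1 there is no tilt.

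**What asking everyone would add.** For a share near one half, exact (Clopper-Pearson) 95% intervals are 18.7% to 81.3% for 5 of 10, 24.7% to 75.3% for 8 of 16, and 40.8% to 58.4% for 66 of 133. The last assumes that all 133 respond, and it widens to 39.8% to 60.2% for 50 of 100. These describe what a survey item could report. They are not a standard the focus groups were meant to meet.

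**The case against.** The strongest reply is that Aim 2d is exploratory and thematic. No preference percentage or test is planned, so a confidence interval is the wrong yardstick for 10 to 16 purposively chosen people. That stands, and precision is not the main argument here. It is also fair that agreeing to one paid research discussion is not the same as preferring group-based care, so r could be close to 1.

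Four stronger readings are tempting, and the documents do not support them.

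- *The preference result will be biased, perhaps enough to reverse the majority.* Any such reversal comes from acceptance rates and a true preference that a reader would have to assume.
- *Inviting only people with raised scores favors group formats.* It does not. It is a reasonable purposive choice for studying barriers to services. It narrows who is heard, but the tilt comes from the group format. That mechanism also gives no reason to expect a tilt in the in-person, phone or video half of the question.
- *Stigma will be under-reported.* Stigma has its own scale in the one-to-one survey, which also covers people who later decline a group. Any loss is confined to the focus-group themes.
- *Attending discloses a positive screen to other members.* That depends on invitation wording that is not shown. Section 6 offers some protection: "We will also encourage participants to use pseudonyms during focus groups and/or interviews", together with a reminder about confidentiality at each session. Pseudonyms would not conceal a selection rule that members already knew, so the wording deserves care, but disclosure is not established.

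**Conclusion.** The point holds as an inexpensive improvement to one exploratory aim. The documents establish that the individual-versus-group question is named only for focus groups, and that a person must have a raised score and accept a recorded group to be heard. It is an inference that the resulting themes lean toward people comfortable in groups. This follows only if such people accept more often (r > 1), and its size cannot be derived from the documents. Separately, the themes may not transfer to decliners or to respondents without raised scores, although the aim is worded for the wider population.

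Neither the randomized comparison nor the HbA1c analysis is touched. The conclusion would weaken if the self-developed help-seeking module already asks about preferred format. The plan should then say so.

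**What to change.** 1. Add two closed items to the telephone survey for every respondent: individual or group; in-person, phone or video. Put them in the current pilot modification, before calls begin. The survey is given once and precedes the groups, so the later interview-guide modification could come after some or all calls.
2. Report the answers descriptively, overall and by raised score and stigma score. Use the focus groups to explain them.
3. Log invitations and refusals, and compare the stigma scores, already collected, of attenders and decliners.
4. Word the invitation so that it does not reveal a screening result.

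A one-to-one phone interview for those who decline a group would be a useful option but is not essential. If calls have already begun, steps 3 and 4 remain possible, and the write-up should limit its preference statements to people who accepted a group.

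The cost is about one extra minute per survey call (our estimate), a simple log and a line in the invitation script.

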5. RISK/BENEFIT ASSESSMENT

5.1 *Potential Risks*

Risks of participation in this study are minimal and unlikely to occur given the safeguards in place. Psychological risks include: 1) the possibility that some participants may perceive some questionnaire or background data assessment as intrusive or causing them to feel uncomfortable; 2) breach of confidentiality. The study involves an intervention designed to enhance adherence to standard diabetes care (e.g., adherence to the prescribed diabetes medication, healthy eating, and physical activity behaviors). If our intervention improves adherence to the medication regimen or if participants make lifestyle changes (e.g., increased physical activity), more episodes of hypoglycemia may result. We will advise participants of the importance of monitoring their blood sugar as suggested by their doctors, and to contact their doctors as soon as they experience low blood sugar.

There is also a potential risk for breach of confidentiality on WeChat. To minimize the risk, we will remind participants that they should call our study phone number for any questions related to the study participation. WeChat will only be used to send education videos. No communication will occur via WeChat. Also, we will remind them at the beginning of the study and during the bi-weekly phone calls about not sending any Protected Health Information via WeChat. In addition, our education videos do not contain any Protected Health Information and it will teach participants about diet, exercise, and stress management in general. Based on our recent completed pilot study (a similar WeChat video study in 30 Chinese immigrants), we did not observe any breach of privacy or confidentiality. All of the study team members received sufficient training on protecting privacy and confidentiality and have extensive experience in working with this hard-to-reach immigrant population. The benefits of receiving these culturally and linguistically tailored education videos outweighed the risks.

5.2 *Benefits*

We do not anticipate that participants will receive any direct benefit from participating. However, information learned during the study may produce benefits for future patients by improving their diabetes care.

